#### **4.6.5.4. Creatinine Clearance and Calcium Excretion**

From the 24-hour urine collection at Day 1 and Month 3, urine sample values will be adjusted for the time period for the sample collection to derive the urine result that is standardized for a 24-hour period. The 24-hour urine results will be summarized descriptively by treatment group and visit. If the end of the collection time of the 24-hour urine is on the same day as the first dose date or within 24 hours from the time of first dose, then the 24-hour urine sample will be considered as a Day 1 sample and will be treated as the baseline sample. Otherwise, the 24-hour urine data will be considered as a post-Day 1 (i.e. post-baseline) sample.

The parameters to be summarized include:

- Urine calcium: creatinine ratio
- 24-hour urine calcium excretion (calcium concentration  $\times$  24-hour urine volume)
- 24-hour urine creatinine excretion (creatinine concentration  $\times$  24-hour urine volume)
- Creatinine clearance (CCr) calculated in two ways:
  - a. Based on 24-hour urine collection
  - b. Based on serum creatinine, calculated using the Cockcroft-Gault estimate, CCr:

$$CCr \text{ (mL/min)} = \{[(140 - age) \times weight \times 1.23] \div SCr\} \times F$$

where:

- *age* = in years
- *weight* = in kilograms
- *F* (constant) = 0.85 for females
- *SCr* = serum creatinine in  $\mu$ mol/L.

The following categories of renal function will be defined:

	Cockcroft-Gault Estimated Serum Creatinine Clearance
Normal	$\geq 90 \text{ mL/min} (\geq 1.5 \text{ mL/s})$
Mild	$\geq 60 \text{ mL/min to } < 90 \text{ mL/min} (\geq 1.0 \text{ mL/s to } < 1.5 \text{ mL/s})$
Moderate	$\geq 30 \text{ mL/min to } < 60 \text{ mL/min} (\geq 0.5 \text{ mL/s to } < 1.0 \text{ mL/s})$
Severe	$\geq 15 \text{ mL/min to } < 30 \text{ mL/min} (\geq 0.25 \text{ mL/s to } < 0.5 \text{ mL/s})$

The number (%) of subjects in each renal function category at each visit and overall (across all visits) will be presented by treatment group. A similar summary table will be presented by treatment group and age group (< 65, 65 - < 75, and  $\geq 75$  years).

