6.2.7.1. Visit 3 (Day 1)

- A 24-hour urine sample will be collected. Subjects will discard the 1st void and begin a 24-hour urine collection on the day prior to the study site visit
- Symptom-driven physical exam, including assessment for potential vertebral fracture
- Collect sample for ADA testing (predose)
- ECG (predose and 1 hour after study drug administration)
- Orthostatic blood pressure and vital signs
- Height
- Weight
- Laboratory testing of serum chemistry, hematology, and urine dipstick
- Serum calcium and albumin (taken predose as part of serum chemistry)
- 1-25 dihydroxyvitamin D
- Dispense study drug
- PK draw between >1 hour to 2 hours after study drug administration
- Clinical assessment of new fractures
- AE and concomitant medication review
- Bone turnover markers (s-PINP and s-CTX)
- Randomization and study drug (abaloparatide-SC or abaloparatide-sMTS) will be assigned through the IRT
- Training for medication self-administration (subjects will be trained on both routes of administration)

- First dose of study drug will be administered by the subject in clinic
- Investigator assessment of signs of local tolerance prior to application of study drug administration, 5 minutes after study drug administration (ie, immediately after patch removal for subjects receiving abaloparatide-sMTS), and at 1 hour following study drug administration
- Subject assessment of symptoms of local tolerance prior to study drug administration, 5 minutes after study drug administration (ie, immediately after patch removal for subjects receiving abaloparatide-sMTS), and 1 hour following study drug administration
- Instruct subject on completion of diary, including daily assessment of local tolerance in between visits
- Subject assessment of patch adhesion (if applicable) immediately prior to patch removal
- Collection of used abaloparatide-sMTS and swab for residual drug testing (for subjects randomized to the abaloparatide-sMTS treatment arm)

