8.4. Description of Statistical Methods

8.4.1. General Approach

Analyses will be presented by treatment group (abaloparatide-SC and abaloparatide-sMTS) and overall, when appropriate. Baseline is defined as the last value obtained prior to the first dose of study drug.

For categorical data, summary tabulations of the number and percentage of subjects within each category of the parameter will be presented. For continuous data, the number of subjects, mean, median, standard deviation (SD), minimum, interquartile range (Q1 and Q3), and maximum will be presented.

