### **3.4. Baseline Definitions**

The baseline value is defined as the last non-missing value obtained prior to the first dose of study drug, including the screening value, if necessary. If a randomized subject is not treated, the baseline value is defined as the last non-missing assessment.

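### The SAP's 24-hour urine rule can label a mostly, and at its edge wholly, post-dose collection as baseline; only descriptive urine summaries are affected

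*SAP*

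**What the plan says.** SAP 4.6.5.4 has a two-part test for the Day 1 urine. A collection qualifies if it ends "on the same day as the first dose date" "or within 24 hours from the time of first dose". If either part is met, the sample "will be considered as a Day 1 sample and will be treated as the baseline sample". Everything else goes the other way: "Otherwise, the 24-hour urine data will be considered as a post-Day 1 (i.e. post-baseline) sample". Collections that do not last exactly 24 hours are kept, because "urine sample values will be adjusted for the time period for the sample collection"; no minimum length is given.

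The general definitions are stricter. SAP 3.4 says: "The baseline value is defined as the last non-missing value obtained prior to the first dose of study drug". Protocol 8.4.1 agrees: "Baseline is defined as the last value obtained prior to the first dose of study drug".

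The protocol also sets the intended timing. At Visit 3 (protocol 6.2.7.1) subjects are to "begin a 24-hour urine collection on the day prior to the study site visit", and protocol 5.6 places the first dose at the site on Day 1. A collection done to plan is therefore wholly or mostly pre-dose.

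**The concern.** Neither part of the urine test asks whether the collection began or ended before dosing. The first goes by calendar date. The second goes by elapsed time without saying in which direction. Post-dose urine can therefore enter a column headed Baseline. SAP Section 1 undertakes to identify substantial departures from the protocol's statistical considerations, but SAP Section 5 does not list this rule.

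The label matters because both arms receive abaloparatide. With no placebo arm, the Day 1 urine is the only scheduled off-drug reference for urinary calcium, and only one other collection is scheduled, at Month 3 (protocol Table 1). Hypercalciuria based on laboratory values is a stated safety evaluation (SAP 1.2.5.2), and protocol 1.1.2.2.1 lists hypercalciuria among the common adverse reactions to the SC product. On-drug urine in the Baseline column could raise the apparent pre-treatment rate and narrow the difference a reader sees between Baseline and Month 3.

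**Working it through.** The plan gives no figure to reproduce here. The check is timing arithmetic at the edges of the rule.

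**Inputs.** The two-part test, the Otherwise clause and the scaling of collections come from SAP 4.6.5.4. The clock time of the first dose is not given. I assume 08:00 to 12:00, since protocol 5.6 suggests morning dosing. Collection lengths other than 24 hours are also assumptions.

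**Formula.** For a collection of length L hours ending e hours after the first dose, post-dose share = min(1, max(0, e) / L).

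**Full collection, L = 24.** All of these count as baseline on a literal reading:

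| End, hours after first dose | 0 | 4 | 8 | 12 | 16 | 20 | 24 |
|---|---|---|---|---|---|---|---|
| Post-dose share | 0% | 16.7% | 33.3% | 50% | 66.7% | 83.3% | 100% |

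**Shortened collections.** The share reaches 100% once e is at least L. A 22-hour collection is wholly post-dose if it ends 22 to 24 hours after the dose, a 20-hour collection if it ends at 20 to 24 hours, and a 16-hour collection if it ends at 16 to 24 hours. All remain baseline under the rule.

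**Same-date part alone.** A full collection ending at midnight on Day 1 is (24 − 8)/24 = 66.7% post-dose for an 08:00 dose, (24 − 10)/24 = 58.3% for 10:00, and (24 − 12)/24 = 50% for noon.

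**What the 24-hour part adds after dosing.** Same-date endings are already covered, so it adds only collections ending on the next calendar day. Those begin where the same-date part stops. For a full collection the share runs from 66.7% to 100% after an 08:00 dose and from 50% to 100% after a noon dose.

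**Direction of the 24-hour window.** Each possible reading leaves a defect on both sides of the dose (full collections, 08:00 dose):

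| Reading | Largest post-dose share accepted as baseline | Wholly pre-dose collection called post-baseline |
|---|---|---|
| After the dose only | 100% | Any that ended on an earlier date |
| Either side | 100% | Ended on an earlier date, more than 24 hours before the dose |
| Before the dose only | 66.7%, through the same-date part | Ended on an earlier date, more than 24 hours before the dose |

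**Where the label is used.** SAP 4.6.5.3 tabulates the number and percentage with hypercalciuria, with Wilson intervals, at Baseline, at Month 3 and overall. SAP 4.6.5.4 summarizes the calcium:creatinine ratio, calcium and creatinine excretion, and urine-based creatinine clearance by visit. The Month 3 percentage uses the Month 3 sample and does not depend on the label given to the Day 1 sample.

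**After the fix.** If baseline requires e ≤ 0, the post-dose share of every baseline sample is 0%.

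**The case against.** The best defence is that SAP 3.4 is written for values taken at a point in time, whereas a 24-hour urine is an interval that may run across dosing. A specific rule may qualify a general one. That is fair, and some overlap rule is needed. But this one has no limit on overlap, does not refer to 3.4, and admits samples with no pre-dose urine at all.

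The second defence is that the protocol is built to avoid the problem. A subject whose collection is mostly or wholly post-dose has departed from the day-before start. This stands: such samples should be uncommon, and a full 24-hour collection is wholly post-dose only at the exact 24-hour edge.

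The third is that little depends on the label. This also stands, and it rules out stronger conclusions a reader might draw:

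- *That the rule hides treatment-emergent hypercalciuria.* The SAP plans no laboratory analysis of incident cases. SAP 4.6.5.3 does not drop subjects positive at baseline and has no shift table or between-arm test. The potentially clinically significant analysis (4.6.5.1) does drop subjects abnormal at baseline, but Appendix C has no criterion for urine calcium:creatinine. Hypercalciuria as an event of special interest is identified from coded adverse event terms (4.6.2).
- *That the rule favours one arm.* Both arms receive active drug under the same collection instructions, and the documents do not say how much one dose changes urinary calcium over 24 hours. Neither the direction nor the size of any between-arm effect can be stated.

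Finally, a strict cut-off that moved every late sample to post-baseline would create a new error. A 24-hour collection ending 5 hours after the dose is 19/24 = 79% pre-dose and does not belong in a post-baseline column either.

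**Conclusion.** The point holds as a minor defect in the baseline definition. The rule as written departs from SAP 3.4 and protocol 8.4.1 and can put urine that is 50% to 100% post-dose into the Baseline column when collection ends on the day after a dose given by noon. It can also label some wholly pre-dose collections as post-baseline.

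The consequence is confined to the descriptive urine results listed above and to the informal Baseline-to-Month 3 comparison. The Month 3 rate, the primary BMD analysis and the non-inferiority conclusion are untouched. How far the baseline figures could move cannot be calculated, because the documents give neither the number of late collections nor the effect of a first dose on urinary calcium. The percentages rest on assumed dose times and, for shortened collections, assumed lengths. That the rule sets no pre-dose requirement rests on the text alone.

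**What to change.** Replace the test in SAP 4.6.5.4 with three classes based on the recorded start and end times:

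1. **Baseline:** the collection ends at or before the first dose, including one that ended on an earlier date.
2. **Straddling:** the collection starts before the first dose and ends after it. Exclude it from the Baseline and Month 3 summaries, or flag it and show the results with and without it.
3. **Post-baseline:** the collection starts at or after the first dose.

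Refer to SAP 3.4 from this section and report the number of straddling collections by arm. The cost is a small programming change and the loss of a few baseline samples. Some of those lost would be nearly on schedule, ending shortly after the dose; showing results both ways keeps their information. No study procedure changes.

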#### **4.6.6. Vital Signs**

Vital signs data, including orthostatic blood pressure, heart rate, body temperature, and respiratory rate, will be summarized by treatment group, visit, and time point using descriptive statistics. Summaries will be presented for the observed value, the change from baseline value, the change from baseline to the worst post-baseline value during the treatment period, and the change from baseline to EOS. If a subject has repeat assessments on the vital signs at a particular scheduled visit/time point, the last non-missing value will be used for the by-visit summary. Unscheduled assessments will be included in the summaries for the worst post-baseline value or PCS, they will not be included in the descriptive by-visit summary tables.

The number (%) of subjects experiencing post-dose orthostatic hypotension will be summarized by treatment group, visit (and across all visits), and time point (including pre-dose). Orthostatic hypotension will be defined as a decrease in systolic blood pressure (SBP) of  $\geq 20 \text{ mmHg}$  from supine to standing or in diastolic blood pressure (DBP) of  $\geq 10 \text{ mmHg}$  from supine to standing. All blood pressure data, including repeat and unscheduled assessments, will be included in determining the incidence of orthostatic hypotension.

The number (%) of subjects experiencing heart rate increase from pre-dose to post-dose and the number of occurrences per subject will be summarized with various threshold values (ranging from  $>5 \text{ bpm}$  to  $>40 \text{ bpm}$ , with threshold values increasing by 5 bpm). The median, minimum and maximum heart rate increase (in bpm) will be provided per threshold value. The number of occurrences per subject will be summarized using the median, minimum and maximum values. All heart rate data, including repeat and unscheduled assessments, will be included in determining the increase from pre-dose in this summary.

The above planned summaries will also be presented by region (North America and Europe).

To evaluate the relationship between age and orthostatic hypotension, the number (%) of subjects with at least one occurrence of post-dose orthostatic hypotension at each visit, timepoint, and overall (across all visits) will be summarized by treatment group and age group (< 65, 65 - < 75, and  $\geq 75$  years).

To evaluate the relationship between age and heart rate increase, the number (%) of subjects with at least one occurrence of heart rate increase from pre-dose to post-dose will be summarized with various threshold values (ranging from  $>5 \text{ bpm}$  to  $>40 \text{ bpm}$ , with threshold values increasing by 5 bpm) by treatment group and age group (< 65, 65 - < 75, and  $\geq 75$  years). Descriptive statistics for heart rate increase per threshold value and the number of occurrences of heart rate increase per subject will be per threshold value will be provided.

All vital signs data will be presented for each subject in a data listing. A listing of subjects with orthostatic hypotension will be presented.

#### **4.6.6.1. Potentially Clinically Significant Vital Sign Values**

Criteria for determining vital signs values that are considered PCS are listed in [Table 5](#).

All vital signs data, including repeat and unscheduled assessments, will be included in determining the incidence of PCS vital sign values. The number (%) of subjects who have at least 1 PCS vital sign values for each vital sign parameter of interest after the first dose of study drug, but had no PCS values at baseline, will be presented by treatment. For the calculation of the percentages of subjects, the denominator will be based on the number of subjects who had no PCS values at baseline and had at least one post-baseline assessment for the specific vital sign parameter of interest.

The above planned summaries will also be presented by region (North America and Europe).

**Table 5: Criteria for PCS of Vital Sign**

Vital Sign	Criterion
Body Temperature (°C)	≥ 39.0
Supine Heart Rate (bpm)	> 100 > 130 < 45
Supine Systolic BP (mmHg)	> 155 < 80
Supine Diastolic BP (mmHg)	> 100
Standing Systolic BP (mmHg)	> 155 < 80
Standing Diastolic BP (mmHg)	> 100

A listing of subjects with any PCS vital sign values will be provided.

#### **4.6.7. Electrocardiogram**

The electrocardiogram (ECG) values collected are heart rate, PR interval, QRS duration, QT, and QTcF (QT corrected by Fridericia's formula). The observed ECG values and change from baseline values, and the change from baseline to the worst post-baseline value during the treatment period will be summarized descriptively for the quantitative ECG results by treatment group, visit, and time point. The overall ECG assessments will be summarized categorically (normal, abnormal without clinical significance, and abnormal with clinical significance) as a shift table by treatment group, study visit, and timepoint. With the exception of change from baseline to the worst post-baseline value during the treatment period, results from unscheduled visits will not be included in the summaries.

Summaries will also be provided for the change from predose values for ECG heart rate, where the predose value is the last value obtained prior to dosing at each visit where ECG is assessed. If a subject has multiple ECG results at a particular visit/time point, the repeat measurement reason will be checked to determine if the first or the last non-missing value will be used for the

summary. If the reason for the repeat assessment is abnormal value, then the first value will be used. If the reason is misplacement of the limb lead electrodes, the last value will be used. Results from unscheduled visits will not be included in these descriptive summary tables.

The number (%) of subjects experiencing heart rate increase from pre-dose to post-dose and the number of occurrences per subject will be summarized with various threshold values (ranging from >5 bpm to >40 bpm, with threshold values increasing by 5 bpm). The median, minimum, and maximum heart rate increase (in bpm) will be provided per threshold value. The number of occurrences per subject will be summarized using the median, minimum and maximum values. All ECG heart rate data, including repeat and unscheduled assessments, will be included in determining the increase from pre-dose in this summary. To evaluate the relationship between age and heart rate increase, the above summary of heart rate increase with various threshold values will also be repeated by treatment and age group (< 65, 65 - < 75, and  $\geq$  75 years).

The number and percentage of subjects with the following QTcF values will be presented by treatment group, visit and time point. Results from repeat/unscheduled visits will be included in shift analyses, as applicable:

- post-baseline QTcF > 450 msec
- post-baseline QTcF > 480 msec
- post-baseline QTcF > 500 msec
- change from baseline > 30 msec in QTcF
- change from baseline > 60 msec in QTcF
- post-baseline QTcF > 500 msec and change from baseline > 60 msec in QTcF

Shift tables from baseline to post-baseline QTcF values using the following categories will be presented for each post-baseline visit and time point. Results from repeat/unscheduled visits will be included in shift analyses, as applicable:

- $\leq$  450 msec and > 450 msec
- $\leq$  480 msec and > 480 msec
- $\leq$  500 msec and > 500 msec.

All ECG data for each subject will be provided in a data listing. Listings will also be provided for those subjects who have any QTcF values greater than 450 msec, 480 msec, and 500 msec, and those with QTcF change from baseline values >30 msec and >60 msec.

Summaries for ECG parameters will also be presented by region (North America and Europe).

## 5. CHANGES FROM THE PROTOCOL-SPECIFIED ANALYSIS

The following changes from the protocol-specified analyses are included in this SAP.

- Antibody Population was added and defined in [Section 2.1](#). All analyses related to the Antibody Population and ADA status will be reported separately.
- The following exploratory efficacy endpoints were added for analysis:
  - BMD responder - proportion of subjects experiencing BMD increase from baseline of >0%, >3%, and >6% at the lumbar spine, femoral neck, and total hip at 3, 6, and 12 months. For the “all sites” analysis by visit and at last assessment in study, subjects who have the pre-specified percentage BMD increase at all 3 anatomical sites at the same visit will be considered responders. A subject must have non-missing BMD results at all 3 anatomical sites at the same visit to be included in the “all sites” analysis. See [Section 4.4.5.1](#).
  - Time to new clinical fracture by 12 months in [Section 4.4.5.2](#).
  - Changes in disease status – The number and percentage of subjects for who disease status has changed from osteoporosis at baseline to osteopenia, normal, or no change at end of study will be tabulated and analyzed using the chi-square test. See definition of osteoporosis, osteopenia and normal in [Section 1.2.5.1](#).
- [Section 3.12](#) defines visit windows for the analyses of BMD, and serum markers of bone metabolism (s-PINP and s-CTX) data to determine the assessment that will be used for a given study visit.
- [Section 4.3.2](#) was added for the analysis of patch adhesion scores for subjects randomized to abaloparatide-sMTS.
- [Section 4.3.3](#) was added for the analysis of patch wear time for subjects randomized to abaloparatide-sMTS.
- [Section 4.3.4](#) was added for the summary of subject exposure to Vitamin D and Calcium supplements.
- [Section 4.3.5](#) was added for the summary of concomitant procedures, which were captured on the Concomitant Procedures Log eCRF as a result of an (other) action taken due to an AE.
- Sensitivity analyses for the primary endpoint were added in [Section 4.4.1.2](#). These sensitivity analyses were also added for the secondary endpoints described in [Section 4.4.2](#).
- Additional analyses to evaluate the impact of the COVID-19 pandemic on study conduct were added for safety and efficacy data, where applicable.

All other statements in this SAP are enhancements to the statistical considerations described in the protocol.

## Appendix A. Conventions for Imputing Missing Dates

### 1. Adverse event (AE) start (onset) date imputation

AE start (onset) date is separated into 3 different data fields, including day, month and year. Completely missing AE start date (i.e., missing day, missing month and missing year) will not be imputed. Partial AE start date will be imputed according to treatment start date as follows in a sequential fashion.

- If AE year is missing, then no imputation
- If AE month and day are missing and
  - if AE year < Treatment year then AE month/day = '01JUL'
  - if AE year = Treatment year then AE month/day = treatment start date+1
  - if AE year > Treatment year then AE month/day = '01JAN'
- If AE day is missing and
  - if AE year < Treatment year then AE day = '15'
  - if AE year = Treatment year and
    - if AE month < Treatment month then AE day = '15'
    - if AE month = Treatment month then AE date = treatment start date+1
    - if AE month > Treatment month then AE day = '01'
  - If AE year > Treatment year then AE day = '01'
- If AE start date is still missing after the above imputation and AE end date is non-missing then AE start date = AE end date.
- If AE start date is still missing after the above imputation then count this AE as a treatment-emergent AE.

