### **4.6.1. Adverse Events**

All AEs will be coded to SOC and PT using MedDRA Version 24.0.

Analyses of AEs will be performed for those events that are considered to be TEAEs. A TEAE is defined as any AE that was absent (i.e., had not occurred) or had resolved prior to the start of study drug, and which occurred on or after the date of the first dose of study drug and within 30 days of the last dose of study drug; or any AE that started prior to the first dose of study drug, was ongoing after study treatment started, and increased in severity after the start of study drug and within 30 days of the last dose of study drug. AEs with missing onset dates will be handled according to the Conventions for Imputing Missing Dates in [Appendix A](#).

TEAEs reported as unanticipated adverse device effects (UADE) or medical device reports (MDR) are those AEs with “Yes” to all of the following three questions on the AE eCRF: “Serious Event?”, “Was AE related to device?”, and “Would you consider this AE unexpected?”. For North American sites, unanticipated device-related SAEs will be reported as UADE for abaloparatide-sMTS, and will be reported as MDR for subjects on abaloparatide-SC. For European sites, unanticipated device-related SAEs will be reported as UADE for subjects on either abaloparatide-sMTS or abaloparatide-SC.

In any tabulation of TEAEs, a subject contributes only once to the count for a given PT and/or SOC, or for a time period category. For summaries by severity, a subject with multiple occurrences of a TEAE will be represented under the most severe occurrence. For summaries by relationship to study drug, a subject with multiple occurrences of a TEAE will be represented under the most related occurrence.

An overall summary of AEs will be presented by treatment group and overall, including the number and percentage of subjects reporting AEs, TEAEs, study treatment-related TEAEs (with probable or possible relationship to study drug), severe TEAEs, treatment-related severe TEAEs, serious TEAEs, treatment-related serious TEAEs, TEAEs leading to study drug interruption, TEAEs leading to study drug withdrawal, TEAEs leading to discontinuation from study, TEAEs related to the device, and TEAEs resulting in death.

The following summaries will be presented:

- TEAEs by SOC and PT
- TEAEs by SOC, PT, and region (North America, Europe)
- TEAEs by SOC, PT and Maximum Severity (mild, moderate, or severe)

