### **3. Other date imputations**

Any event with a partial date that requires imputation but has no specific imputation rule will be imputed as follows:

- If the day is missing, then impute the day as '01'
- If the month is missing, then impute the month as 'JUL'
- If the imputation of a start date causes the start date to be post the non-missing end date, then the start date will be imputed as the end date.
- If the imputation of a start date causes the start date to be prior to the start of treatment (but the event should happen post-baseline), then the start date will be imputed as "treatment start date + 1."
- Any date cannot be imputed past the date of death. When this happens, the date will be imputed as the date of death.

**Appendix B. Algorithm to Identify Critical Protocol Deviations that Exclude Subjects from the Per-Protocol (PP) Population**

The below algorithm outlines the criteria for identifying critical protocol deviations. Subjects with at least one of these critical protocol deviations will be excluded from the PP population.

- A. Deviations of subject eligibility (Inclusion/Exclusion criteria) that will result in exclusion from PP population (refer to the protocol for the complete text of each inclusion/exclusion criterion below):
  - 1. Inclusion Criterion #2: Less than 5 years postmenopausal.
  - 2. Inclusion Criterion #3: A BMD T-score outside the required range or fracture criteria not met.
  - 3. Exclusion Criterion #1: History of more than 4 spine fractures, mild or moderate, or any severe fractures.
  - 4. Exclusion Criterion #2: Presence of abnormalities of the lumbar spine that would prohibit assessment of spinal bone mineral density (BMD).
  - 5. Exclusion Criterion #3: Unevaluable hip BMD or subjects who have undergone bilateral hip replacement.
  - 6. Exclusion Criteria #4, #5, #6: Diseases and treatments affecting bone strength.
  - 7. Inclusion Criterion #5: Laboratory tests affecting the bone strength.
  - 8. Exclusion Criteria #16, #17, #18, #19, #20, #21, #22, #23, #24 and #26: Prior treatment with bone-acting agents within the specified time periods.
- B. Deviations of study drug administration that will result in exclusion from PP population:
  - 1. Duration of study drug exposure is less than 3 months (90 days)
  - 2. Compliance to study drug administration < 80%
- C. Deviations of efficacy measurements that will result in exclusion from PP population:
  - 1. Lumbar spine BMD is missing at baseline

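### Two AE onset-date rules ignore a known end date, so events that were over before first dose become treatment-emergent with a negative duration

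*SAP*

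**What the plan says.** SAP Appendix A.1 has eight branches for a partial AE onset date, and two of them assign the day after first dose. When month and day are both missing, the rule is "if AE year = Treatment year then AE month/day = treatment start date+1". When only the day is missing and the year matches, it is "if AE month = Treatment month then AE date = treatment start date+1". Neither carries a condition on the end date.

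A.1 uses the end date once: "If AE start date is still missing after the above imputation and AE end date is non-missing then AE start date = AE end date".

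Appendix A.3 does compare an imputed start with the end date. Its rule begins "If the imputation of a start date causes the start date to be post the non-missing end date", and it then resets the start to the end date. The lead-in to A.3 sets its scope: "Any event with a partial date that requires imputation but has no specific imputation rule will be imputed as follows".

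SAP 4.6.1 requires of a new treatment-emergent AE (TEAE) an onset "which occurred on or after the date of the first dose of study drug and within 30 days of the last dose of study drug", and sends missing onset dates to Appendix A. SAP 4.6.2 summarises onset time and duration for treatment-emergent AEs of special interest (AESIs). It covers a missing stop date, but not a stop date earlier than the start.

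**The concern.** Protocol 7.1 collects AEs from consent, so events before treatment are in the database. SAP 4.6.1 expects them, since it plans a table of non-TEAEs. Treating an event of unknown timing as treatment-emergent is a sensible conservative default. It is not sensible when the recorded end date shows that the event was over before the first dose.

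Such an event moves from the non-TEAE table into the TEAE tables. Its imputed onset is Day 2, so it falls in the earliest onset category of SAP 4.6.1 and, if it is an AESI, in the 2-3 day onset group of SAP 4.6.2. A pre-treatment event is then shown as an early reaction to study drug. For an AESI, the negative duration fits none of the planned duration groups. It also lowers the subject's average duration when there is more than one occurrence.

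**Working it through.** **1. Can the records exist?** Screening lasts up to 2 months, Pretreatment lasts 1 week, and a month is 30 days (protocol 3.1). The pre-dose collection period is therefore up to about 2 × 30 + 7 = 67 days. It can include days in the calendar month, or the calendar year, of first dose.

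**2. Does any other rule catch them?**
- The end-date rule in A.1 applies only when the onset is still missing after imputation. The two branches at issue have just assigned a date, so it cannot apply.
- The check in A.3 is limited to dates with no rule of their own. AE onset has one.
- The TEAE definition tests onset, and where onset is missing it takes the onset from Appendix A. It has no separate test on the end date.

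**3. Worked cases.** The plan gives no figure to reproduce, so the A.1 rules were applied literally to illustrative dates. Two assumptions are made:
- First dose is 20 March 2020, so treatment start + 1 is 21 March 2020.
- Duration = end - start + 1. The SAP gives no AE duration formula; without the + 1 each value is one day lower.

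| Case | Recorded onset | Recorded end | Imputed onset | TEAE? | Duration (days) |
|---|---|---|---|---|---|
| a | March 2020, day unknown | 10 March | 21 March | Yes | -11 + 1 = -10 |
| b | March 2020, day unknown | 19 March | 21 March | Yes | -2 + 1 = -1 |
| c | 2020 only | 5 February | 21 March | Yes | -45 + 1 = -44 |
| d | Wholly missing | 10 March | 10 March | No | 0 + 1 = 1 |
| e | February 2020, day unknown | 5 February | 15 February | No | -10 + 1 = -9 |
| f | March 2020, day unknown | 20 March (Day 1) | 21 March | Yes | -1 + 1 = 0 |

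Cases a to c are false TEAEs. Case d is the event of case a with less onset information, and it is classified correctly. That contrast marks a gap in the rule and not a deliberate conservative choice. Case e shows that another branch can also place onset after the end, but without making the event treatment-emergent. In case f the TEAE status is right and only the date order is wrong.

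**4. The same cases with the A.3 check added to A.1.** In a to c, onset becomes 10 March, 19 March and 5 February. None is a TEAE, and each duration is 1 day. Case d does not change. Case e starts on 5 February with duration 1. Case f starts on 20 March, remains a TEAE and has duration 1. An event with onset 2020 only and no end date still gets 21 March and remains a TEAE, so the default is kept where timing is truly unknown.

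**The case against.** The strongest reply concerns size. Only two of eight branches are affected. The site must have recorded when the event ended but not the day it began, for an event within about 67 days of first dose. Subjects are asked about AEs at every visit, and missing or discrepant data are queried (protocol 9.7), so few such records may survive to analysis, perhaps none. Any error overcounts TEAEs, by the same rule in both arms, in a safety analysis that is mainly descriptive. All of this stands, and it sets the severity.

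The claim about durations also has to be kept narrow. Administration-site and skin AESIs concern the study-drug site and cannot precede dosing. The exposed types are hypersensitivity and the SAP's other AESIs, such as nausea, tachycardia and orthostatic hypotension.

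Two arguments would remove the problem altogether. One is that the TEAE definition governs, so an event that ended before dosing fails it whatever onset is imputed. But 4.6.1 itself sends missing onset dates to Appendix A, and a program that follows the SAP will test the imputed date. The other is that the A.3 check was meant to be general. That may be so, and the rule nearby that bars any date after death is worded generally. The lead-in still says otherwise, and a programmer should not have to guess.

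**Conclusion.** The concern holds. Followed as written, Appendix A.1 gives the wrong classification for every AE that has a partial onset in one of the two same-year branches and a recorded end before first dose, and it leaves a stop date before the start date. The number of records cannot be derived from the documents; it is probably small. The primary BMD endpoint and the non-inferiority conclusion are not touched, and no safety conclusion is shown to change. The conclusion rests on a literal reading of the scope of A.3. The example dates and the duration formula are assumptions that affect only the illustrative durations, not the finding. This is a minor correction worth making because the result is impossible on its face.

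**What to change.** Add one line to Appendix A.1, after the partial-date branches: if the imputed onset is later than a fully recorded end date, set onset to that end date. State that an event with a recorded end before first dose is not a TEAE. Keep treatment start + 1 when there is no end date, or when the end date is on or after the imputed onset.

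Limit the line to fully recorded end dates. A.1 has no rule for a partial AE end date, so A.3 could set a missing end day to the first of the month. That imputed date would not show that the event was over before dosing.

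The cost is one sentence and one line of code, copying a rule the sponsor already has in A.3. No new data are needed, and no other table specification changes.
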